The central hypothesis tested in this study is whether a 4-day antibiotics course is equivalent to an 8-day course for post-drainage primary and secondary clinical outcomes.

Primary outcomes:

- readmission rate

Secondary Outcomes:

- length of stay (LOS)
- rate of post-drainage surgical site infection until 30 days after discharge
- rate of post-drainage abdominal abscess until 30 days after discharge
- secondary site infections

C. Methods

C.1. Study Design

This research proposes a randomized, prospective, equivalence trial design to test the research hypothesis. This study will demonstrate no difference in clinical outcomes between the 4-day antibiotic course and the 8-day course. The study will include 342

IRB#: 17-055

Title: A prospective randomized trial of antibiotic duration in post-appendectomy abscess

PI: [name]

Col's: [name], [name]; [name]; [name]; [name]; [name]; [name]; [name] [name]; [name]; [name].

pediatric patients (includes 10% oversampled) ages 2 through 17 years treated from February 1, 2019 onward until the study cohorts have been filled. This study is based on an expectation of 90% success (10% readmitted) in arm A=10% and expectation of 90% success (10% readmitted) in arm B =10%. The clinical difference in primary outcome between the two groups that we are prepared to accept is equal or greater than 10% (i.e., clinically, we are willing to accept 10 children per 100 who may have benefited from the long course but received a short course to achieve 90% of children who received the short course and would not have benefitted from a long course). The sample size needed to attain a power of 0.80 at alpha=0.05 is 342 (171 in each arm, which includes a 10% attrition rate). The risk of type I error is 1-0.95 (alpha=0.05); power=0.80. The study will proceed until 171 patients are consented for each arm. Study personnel will perform an interim analysis of the data approximately halfway through study enrollment.

Definition of perforated appendicitis - Perforated appendicitis is defined as a visible hole or feces found in the abdomen at laparoscopy. ***For purposes of research, either the hole or feces is photographed, and "hole," "feces/stool in the abdomen," or other note describing perforation will need to be specifically described in the operative report.***

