Based on estimates from the Division of Pediatric Surgery, PCH performs approximately 1000 laparoscopic appendectomies annually. Approximately one-third of these appendectomies (300) are perforated; about 10%-20% of these 300 perforated patients (30-60) will develop a post-surgical abscess treated with a percutaneous drain and IV antibiotics.

Screening - The study population is comprised of patients who, upon admission, are diagnosed with perforated appendicitis and who, after laparoscopy, form an abscess (while still in hospital or discharged and then readmitted with abscess), and are treated with percutaneous drainage and IV ceftriaxone/metronidazole or other broad spectrum antibiotic equivalent per hospital standard of care. Screened patients will be assigned a screening ID, which will be maintained in a screening log.

Randomization - Once eligibility for study inclusion is determined at the time of drainage, the patient will be consented by the principal investigator or sub-investigator and assigned a study number. A block randomization strategy will be used based on a random number generator and applied after consent by site to assign patients to either the control (8-day) or experimental (4-day) arm of the study. All patients will be randomly assigned by patient study numbers. A current randomized trial underway at Phoenix Children's Hospital requires photography to confirm a diagnosis of perforation (IRB 17-011). We propose to follow the same approach for verifying perforated appendicitis across WSPRC institutions in this study. When possible, the hole or feces will be

IRB#: 17-055

Title: A prospective randomized trial of antibiotic duration in post-appendectomy abscess

PI: [name]

Col's: [name], [name]; [name]; [name]; [name]; [name]; [name]; [name] [name]; [name]; [name].

photographed. If not, "hole," "feces/stool in the abdomen," or other note describing perforation will need to be specifically described in the operative report. The two study arms will include some patients with abscess that has been confirmed though CT or ultrasound as part of standard of care prior to study participation. We will include CT/ultrasound results as part of data collection.

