Col's: [name], [name]; [name]; [name]; [name]; [name]; [name]; [name] [name]; [name]; [name].

It is estimated that it will take about 6 years for PCH to fill the study arms; interim analysis will be performed when study cohorts are half-filled. In order to complete this and other planned pediatric appendicitis studies more quickly, we are planning to add other study sites through the Western Surgical Research Consortium. The multisite approval process will be facilitated by Streamlined Multisite Accelerated Resources for Trials (SMART) IRB certification. With participation from the nine hospitals in the Western Surgical Research Consortium, we would expect to fill the trial cohorts in approximately 2 years.

C.4. Data Analysis Plan

The study will describe patient and clinical characteristics related to laparoscopy among study cohorts (e.g., age, BMI, gender, maximum temperature upon admission, diarrhea at presentation, duration of symptoms, and white blood cell count); patient recovery and abscess formation (e.g., time to abscess, abscess size if available, time to regular diet, and LOS after the drainage); primary clinical outcome (readmission); and secondary clinical outcomes (LOS, total visits after discharge, post-drainage occurrence of abscess, and post-drainage secondary infection).

All data will be described using descriptive statistics, including means, standard deviation, and proportions. Differences among treatment cohorts and on clinical outcomes will be assessed using parametric and non-parametric tests as appropriate. Factors confounding outcomes will be identified *a priori* from research and empirically via correlational analysis for continuous measures or through non-parametric techniques for discrete variables with a Bonferroni correction for multiple comparisons among families of statistical tests. Binomial logistical regression will also be used where appropriate. Unadjusted odds ratios will be used to identify variables of interest and confounding effects for discrete dependent variables of interest. Adjusted odds ratios will be used to compare differences among study cohorts and covariates (e.g., age, gender, white blood cell count, and BMI), interactions, and confounders as appropriate. Statistical significance will be defined as an alpha of 0.05, with two-sided alternative hypothesis and a Bonferroni correction for multiple comparison. Data analysis will be performed using SPSS and R.

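### C.4 gives no equivalence analysis for the 10-point margin behind the 342 patients, and does not say whether the comparison of arms is stratified by site

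*Combined protocol and SAP*

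**What the plan says.** All references are to the combined protocol and SAP.

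- **Design and size (C.1 Study Design).** The trial is an equivalence trial with 10% readmission expected in each arm and a 10-point difference as the acceptable limit, which I read as the equivalence margin. "The sample size needed to attain a power of 0.80 at alpha=0.05 is 342 (171 in each arm, which includes a 10% attrition rate").
- **Randomisation (C.1).** "A block randomization strategy will be used based on a random number generator and applied after consent by site to assign patients" to the 8-day or 4-day arm. No block size is given. Section E.3 describes the assignment again and mentions neither blocks nor site.
- **Sites (C.3 Data Collection).** The lead hospital would need about 6 years alone, so "we are planning to add other study sites through the Western Surgical Research Consortium". The 2-year estimate is conditional: "With participation from the nine hospitals in the Western Surgical Research Consortium".
- **Analysis (C.4 Data Analysis Plan).** "Differences among treatment cohorts and on clinical outcomes will be assessed using parametric and non-parametric tests as appropriate". "Adjusted odds ratios will be used to compare differences among study cohorts and covariates (e.g., age, gender, white blood cell count, and BMI"), together with interactions and confounders where suitable. "Statistical significance will be defined as an alpha of 0.05, with two-sided alternative hypothesis and a Bonferroni correction for multiple comparison".

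C.4 is the only analysis text. It names no risk difference, no confidence interval, no rule that refers to the margin, and no role for site.

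**The concern.** An equivalence claim needs an interval for the difference that lies inside the margin. A test of difference that is not significant does not supply this, and an odds ratio is not on the scale of a 10-point margin. C.4 therefore does not yet contain the analysis for which the trial was sized.

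Two choices are left open as a result.

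1. **Confidence level.** The sample size matches one level, while C.4's significance sentence, if carried over to an interval, suggests another. Bonferroni is applied without saying whether it touches the single primary comparison. The stated power depends on the answer.
2. **Site.** If randomisation is blocked within site, the usual convention is to analyse by those strata. C.4 neither specifies nor excludes this. Study personnel perform the interim analysis, so a choice left open now could be made by people who have seen results.

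**Working it through.** **1. The plan's own sample size.** Inputs from C.1: p = 0.10 in both arms, margin 0.10, power 0.80, alpha 0.05, 10% attrition. For two one-sided tests at 0.05 each, with a true difference of zero:

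n per arm = 2p(1−p)(z₀.₉₅ + z₀.₉₀)² / margin² = 2 × 0.09 × (1.645 + 1.282)² / 0.10² = 154.1

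154 / 0.9 = 171 per arm, or 342 in total. (Rounding up to 155 and adding 10% gives 155 × 1.10 = 170.5, also 171.) The stated figure is reproduced. Two one-sided tests at 0.05 are the same as asking whether a 90% interval lies inside ±10 points.

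Other readings fit less well. Non-inferiority gives 124 to 125 per arm (one-sided 0.05) or 157 to 158 (one-sided 0.025), and two-sided superiority of 10% against 20% gives 219 to 222. A one-sided superiority test of 10% against 20% comes close, at 173 to 175, but contradicts the equal rates that C.1 assumes.

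**2. The same size with a 95% interval.** The standard error at 154 per arm is √(2 × 0.09 / 154) = 0.03419.

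- 90% interval: power = 2Φ(0.10/0.03419 − 1.645) − 1 = 0.80.
- 95% interval: power = 2Φ(0.10/0.03419 − 1.960) − 1 = 0.665.
- Evaluable size needed for 80% power with a 95% interval: 2 × 0.09 × (1.960 + 1.282)² / 0.01 = 189.1 per arm, about 210 with attrition (189 / 0.9).

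A Bonferroni adjustment of the primary comparison would lower power further; C.4 gives no family size from which to compute it.

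**3. Site, by large-sample formula.** The documents give no between-site variation in readmission, so I assume SDs (s) of 3, 5 and 7 points around 10%. The stratified standard error is the unstratified one times √(1 − s²/0.09), that is 0.995, 0.986 and 0.972. The 90% half-width at 154 per arm is 1.645 × 3.419 = 5.62 points, and becomes 5.60, 5.54 and 5.47.

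**4. Site, by simulation.** 342 randomised, permuted blocks of 4 within nine sites, 10% random loss, beta-distributed site rates, 200,000 trials per setting. The crude Wald interval is compared with Mantel-Haenszel weights and the Sato variance, with sites under 10 patients pooled. Site sizes are assumptions: equal (38 each); uneven (120, 70, 50, 36, 26, 16, 12, 8, 4); very uneven (180, 70, 40, 24, 10, 7, 5, 4, 2). The 120 is the top of C.1's yearly estimate for the lead hospital over 2 years: "about 10%-20% of these 300 perforated patients (30-60) will develop a post-surgical abscess", so 2 × 60.

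Power (%), without / with site:

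| Site SD (points) | Equal | Uneven | Very uneven |
|---|---|---|---|
| 0 | 79.7 / 79.6 | 79.6 / 79.5 | 79.7 / 79.6 |
| 3 | 80.0 / 80.1 | 79.9 / 80.0 | 79.9 / 79.9 |
| 5 | 80.1 / 80.7 | 79.9 / 80.4 | 79.8 / 80.2 |
| 7 | 80.4 / 81.7 | 80.2 / 81.3 | 80.0 / 80.9 |

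Blocks of 8 gave similar changes. Three further results show what the gain is:

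- The empirical SDs of the crude and stratified estimates agree to within 0.0001, so precision is unchanged.
- With no true difference, the mean reported standard error divided by the empirical SD is about 0.99 to 1.02 for the crude analysis and 0.98 to 1.00 for the stratified one. The stratified error is on average no better calibrated.
- False equivalence at a true 10-point difference is 5.0 to 5.3% without site and 5.1 to 5.4% with site.

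The extra power and the extra false equivalence are the same effect: a slightly smaller reported standard error.

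**The case against.** The strongest objection concerns site. Blocking has already given the estimate whatever precision it can, the crude standard error is at least as well calibrated at this size, and in an equivalence trial the error that matters moves slightly the wrong way. The premises are also conditional. The randomisation sentence could mean that each site applies the scheme, E.3 does not settle it, and nine hospitals is an expectation. With one site, the stratified and crude analyses coincide. C.4's covariate list is open, so site is not ruled out. All of this stands. It removes precision and standard-error calibration as reasons to stratify. It leaves two modest reasons: following the randomisation, and fixing a discretionary choice before data are seen.

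On the equivalence rule, it can be said that C.1 already states the design and margin, and that C.4's alpha sentence was written for tests in general. That is fair, and it is why C.4 cannot be said to adopt a 95% interval. It does not supply the missing rule.

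A reader might infer three stronger things. The first is that leaving site out makes the analysis invalid or wasteful; the calculations show otherwise. The second is that the trial has only 66.5% power; that follows only if a 95% interval is used, which the documents do not say, and their own sample size points to 90%. The third is that a non-significant test will be declared equivalence; C.4 gives no decision rule of any kind, so this cannot be read from it.

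**Conclusion.** The point holds in two parts of unequal weight.

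The weightier part is that C.4 lacks the primary equivalence analysis, and that its two-sided 0.05 with Bonferroni is not reconciled with the sample size. The 342 patients fit a 90% interval (80% power); a 95% interval at the same size gives 66.5%. This rests on C.1's own rates and attrition, and on reading the 10 points as the margin.

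The minor part is that the blocking by site is not carried into the comparison of arms. Stratifying changes power by 0 to +1.3 points at assumed site SDs of 3 to 7 points and by −0.1 to −0.2 point if sites do not differ, with up to about 0.3 point more false equivalence. Site SDs, site sizes and block sizes are assumptions. Stratification is worth adding as alignment and pre-specification only.

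**What to change.** Add to C.4:

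> The primary comparison is the difference in readmission risk between arms, stratified by site (Mantel-Haenszel weights, Sato variance), with its 90% confidence interval compared with ±10 percentage points. Small sites are pooled by a rule fixed before the interim analysis. If one site enrols, the unstratified difference is used. Bonferroni does not apply to this single comparison.

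A workable pooling rule, with the cut-off as an example: sites that randomise fewer than 10 patients form one stratum, and if that stratum has no patient in one arm it joins the smallest remaining site. Pooling matters because, in the very uneven layout, 48% (blocks of 4) to 59% (blocks of 8) of simulated trials had a site with an empty arm.

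If the investigators prefer a 95% interval, they should restate power as about 66% at 154 evaluable per arm, or revise the sample size.

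The stratification belongs to the risk difference. A dummy for each site should not be added to the adjusted logistic model: 308 × 0.10 gives about 31 readmissions, against 1 arm + 4 covariates + 8 site terms = 13 parameters, or 2.4 events each.

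The cost is a short clause and a few lines of R, which C.4 already names. Site is known from randomisation, so no patients, visits or data items are added. The statistical price is the small change in power and false equivalence given in the verdict.

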PROTOCOL

PROTOCOL TITLE	A prospective randomized trial of antibiotic duration in post-appendectomy abscess
PROTOCOL NUMBER	17-055
STUDY DESIGN (PHASE)	Prospective randomized
PROTOCOL VERSION	Version 5 Dated September 25, 2019
NCT NUMBER	NCT03795194
SPONSOR	[name] Phoenix Children's Hospital [name]
PRINCIPAL INVESTIGATOR	[name]

IRB#: 17-055

Title: A prospective randomized trial of antibiotic duration in post-appendectomy abscess

PI: [name]

Col's: [name], [name]; [name]; [name]; [name]; [name]; [name]; [name] [name]; [name]; [name].

Abstract

Appendicitis is a very common surgical problem in children. Although the rates of post-appendectomy abscess in simple appendicitis are less than 1%, the rates of post-appendectomy abscess in complicated appendicitis are not well-described.⁵⁻⁸ Complicated appendicitis includes patients who present with a visible perforation and/or feces in the abdomen, a primary abscess, phlegmon, gangrene, or all of the above.²⁻⁴ Research suggests that neither the type of the antibiotic therapy nor duration of treatment has a significant impact on reducing the risk of post-operative abscess for patients who present with any form of complicated appendicitis.⁷ However, the lack of an evidence-based definition of perforated appendicitis has undermined the reliability of most research results because the study populations may have included non-complicated patients. In this study, we propose to assess the equivalence of an 8-day fixed course and a fixed 4-day course of antibiotics at drainage for perforated patients who develop a post-surgical abscess. We are proposing to study 342 pediatric patients (includes 10% oversampled) ages 2 to 17 years at institutions in the Western Surgical Pediatric Research Consortium (WSPRC) who are diagnosed with perforated appendicitis, treated laparoscopically, **and form an abscess post-laparoscopy**. We hypothesize that the 8-day course of antibiotics is equivalent to the 4-day course on the primary clinical outcome (i.e., readmission rate) and secondary outcomes: length of stay (LOS) upon readmission; rate of abscess from drainage until 30 days after discharge, and wound infection from drainage until 30 days of discharge. This research will provide an ongoing contribution to the clinical management of complicated pediatric appendicitis and antibiotic stewardship.

A. Introduction/Background

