Antibiotic regimen - All post-laparoscopic abscess patients will receive the standard of care for antibiotic therapy—IV ceftriaxone/metronidazole or other broad spectrum antibiotic equivalent—until afebrile (38.5° C) and tolerating food for 24 hours (i.e., without vomiting). CBC panels are also standard of care and may be drawn multiple times during the patient's stay. Standard of care at discharge includes prescribed oral, empiric, antibiotic therapy (PO), such as ampicillin/clavulanate or other broad spectrum antibiotic. The choice and the duration of broad spectrum antibiotic prescription are at the surgeon's discretion.

In this study, all patients will be treated with the hospital standard of care and receive in-patient treatment for abscess until afebrile and tolerating food for 24 hours. After percutaneous drainage of the abscess, the patient will be randomly assigned to receive either an 8-day regimen (arm A) or a 4-day regimen (arm B) of antibiotics (Diagram 1). Patients will remain on IV ceftriaxone/metronidazole or other broad spectrum antibiotic equivalent until afebrile and tolerating food for 24 hours. Patients will complete their assigned 4- or 8-day regimen with oral ampicillin clavulanate or other broad spectrum antibiotic equivalent. If patients are not afebrile at the completion of their assigned regimen, prescribing an extended course of antibiotics is at the discretion of the treating surgeon. A prescribed oral course of antibiotics may be finished in the hospital or at home if patient is discharged.

Ampicillin and clavulanate have been safely utilized in previous pediatric research.^{5,10,14,11} These antibiotics have demonstrated clinical equivalence in both retrospective studies and prospective trials.^{9,11} This randomized trial is the first to address duration of antibiotic treatment in pediatric patients diagnosed with perforated appendicitis and who form a post-laparoscopic abscess. Pediatric patients who are allergic to ampicillin will be prescribed another broad-spectrum antibiotic (e.g., gentamycin/clindamycin or ciprofloxacin) at the discretion of the treating surgeon.

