Two arms are proposed for the study following the protocol implemented for adults in a recent randomized trial.²¹ In the control arm, patients will be treated with an 8-day course of antibiotics, and in the experimental arm, patients will be treated with a 4-day course of antibiotics. The randomized trial should control for all confounding effects. In addition,

IRB#: 17-055

Title: A prospective randomized trial of antibiotic duration in post-appendectomy abscess

PI: [name]

CoI's: [name], [name]; [name]; [name]; [name]; [name]; [name]; [name] [name]; [name]; [name].

we will collect clinical data on the pre-operative, peri-operative and post-operative antibiotic treatment and number of days on antibiotic therapy prior to discharge to manage this potential confounder *post hoc*.

There is a low probability of study attrition or loss to follow-up. As the primary treatment provider in a study with a short (30-day) follow-up period for readmission, we do not expect significant attrition. Follow-up will entail tracking all patients from the initial study who return to the hospital for complications related to the procedure within 30 days of discharge. All complications, including those requiring readmission, will be included in the follow-up. All study patients will be assessed for primary and secondary clinical outcomes. Complications associated with surgically treated acute appendicitis based on the National Surgery Quality Improvement Program criteria (available at <http://nsqip.healthsoftonline.com/hsi/>) include (1) wound infection, (2) abscess, (3) post-discharge small bowel obstruction, (4) hernia, (5) length of hospital stay of greater than 4 days, and (6) death.

[figure not shown]
IRB#: 17-055

Title: A prospective randomized trial of antibiotic duration in post-appendectomy abscess

PI: [name]

CoI's: [name], [name]; [name]; [name]; [name]; [name]; [name]; [name] [name]; [name]; [name].

Diagram 1: Treatment arms for randomized trial of an 8-day antibiotic treatment vs. 4-day treatment of post-laparoscopic abscess formation in pediatric complicated (perforated) appendicitis.

* If febrile after assigned course of antibiotics (i.e., 8 days or 4 days) is completed, extended antibiotic treatment will be up to the treating surgeon.

†Patient may be discharged before 8- or 4-day course is completed and may finish antibiotics at home.

IRB#: 17-055

V5 9/25/2019

IRB#: 17-055

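### For a child who is afebrile but not yet tolerating food when the assigned course ends, the protocol's IV-continuation rule and its fixed 4- or 8-day course give opposite instructions

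*Combined protocol and SAP*

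**What the plan says.** Four places bear on when antibiotics end.

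- **IV continuation.** C.1 (Antibiotic regimen) says of study patients: "Patients will remain on IV ceftriaxone/metronidazole or other broad spectrum antibiotic equivalent until afebrile and tolerating food for 24 hours". The standard-of-care paragraph just above has the same criterion with a gloss: "until afebrile (38.5° C) and tolerating food for 24 hours (i.e., without vomiting". Section D.1 repeats the criterion as standard of care and says all study patients receive that care. None of these sentences mentions day 4 or day 8.
- **Assigned duration.** The Abstract's aim is to "assess the equivalence of an 8-day fixed course and a fixed 4-day course of antibiotics at drainage". C.1 adds: "Patients will complete their assigned 4- or 8-day regimen with oral ampicillin clavulanate or other broad spectrum antibiotic equivalent". IV days therefore count toward the assigned total.
- **Extension, in the text.** C.1 leaves this choice to the surgeon: "If patients are not afebrile at the completion of their assigned regimen, prescribing an extended course of antibiotics is at the discretion".
- **Extension, in the diagram.** The Diagram 1 footnote: "If febrile after assigned course of antibiotics (i.e., 8 days or 4 days) is completed, extended antibiotic treatment will be up to the treating surgeon".

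The continuation criterion has two parts, fever and food tolerance, with a 24-hour period attached. The extension criterion has one part, fever.

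**The concern.** The randomized factor is antibiotic duration, so the rule that ends the course defines what is being compared. If an unrecovered child stays on IV drug at one site and stops at another, and both can cite the protocol, the 4-day arm is not the same regimen everywhere. C.3 foresees nine hospitals, so the wording will be interpreted by several teams. No text shows that they would in fact differ.

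The direction also matters. Section C.1 sets out to show no difference. Treatment beyond the assigned day in the short arm makes the arms more alike, which favours that conclusion. The analysis plan does little to offset this: it defines no analysis sets, and C.1 proposes only post hoc handling of antibiotic days before discharge, although the course may be finished at home.

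**Working it through.** **1. The rules side by side.** Take a child on the last day of the assigned course.

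| State of the child | IV-continuation sentence | Assigned course | Extension clause |
|---|---|---|---|
| Afebrile and tolerating food for 24 hours | met; already switched to oral | ends | not needed |
| Afebrile, not yet tolerating food | IV continues | ends | not triggered |
| Still febrile | IV continues | ends | surgeon may extend |
| Fever settled within the last 24 hours, food tolerated for 24 hours | depends on what the 24 hours modifies | ends | not triggered |

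Row 1 has no conflict. Row 2 is a direct conflict that no stated clause resolves. In row 3 the wording is mandatory in one sentence and discretionary in the other. Row 4 is a conflict only if the 24 hours applies to being afebrile as well as to food, and the word order allows either reading.

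**2. The plan's own figure.** Inputs from C.1: 10% readmission in each arm, margin 10 points, alpha 0.05, power 0.80, attrition 10%. Two one-sided tests at 0.05 give n = 2 × 0.1 × 0.9 × (1.645 + 1.282)² / 0.10² = 154.1, so 155 per arm. Then 155 × 1.10 = 170.5, so 171 per arm and 342 in total, as stated. The calculation makes no allowance for a narrowed contrast.

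**3. Which arm is affected more.** Let T be the days from drainage until the IV criterion is met. With randomized arms and any common distribution of T, P(T > 4) is at least P(T > 8). This needs no further assumption.

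**4. Size of the contrast (assumed).** The documents give no recovery times. If the IV sentence always governs, the mean course is E[max(c, T)] = c + ∫ P(T > t) dt from c upward, with c = 4 or 8. For an exponential T with mean m = median / ln 2, this is c + m·exp(−c/m).

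| Assumed T | P(T > 4) | P(T > 8) | Mean days, 4-day arm | Mean days, 8-day arm | Contrast |
|---|---|---|---|---|---|
| Exponential, median 2 | 25% | 6% | 4.72 | 8.18 | 3.46 |
| Exponential, median 4 | 50% | 25% | 6.89 | 9.44 | 2.56 |
| Weibull shape 2, median 2 | 6% | 0.002% | 4.04 | 8.00 | 3.96 |
| Weibull shape 2, median 4 | 50% | 6% | 5.02 | 8.08 | 3.06 |

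The intended contrast is 8 − 4 = 4.0 days. The result depends heavily on the assumed shape as well as the median.

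**5. What a narrowed contrast could do (assumed).** Suppose the true readmission rates under the two pure regimens are 10% (8-day) and 20% (4-day), a difference equal to the margin. Suppose a fraction f of the 4-day arm is extended and takes the full 8-day risk. The expected difference is 10 × (1 − f) points. With 155 per arm, the probability of declaring equivalence is:

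| f | Expected difference (points) | P(declare equivalence) |
|---|---|---|
| 0 | 10 | 5.0% |
| 5% | 9.5 | 6.4% |
| 10% | 9 | 8.1% |
| 20% | 8 | 12.7% |
| 30% | 7 | 19.0% |

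This counts as error only if the claim concerns fixed courses. If the claim concerns a 4-day course with extension when needed, the diluted difference is the one of interest.

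**The case against.** The strongest reply is that the IV sentence is a route rule. The paragraph runs in order: randomize, give IV drug until recovery, complete the assigned days orally, then deal with fever at the end. Read this way, it times an IV-to-oral switch inside a fixed total. That stands for every child who recovers before the assigned day. It does not reach the child who has not recovered by then, because no text says that the switch criterion lapses when the course ends.

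For the febrile child, the specific clause can fairly be taken to override the general one, and a surgeon who extends satisfies both. That largely stands; what remains is a mismatch between mandatory and discretionary wording.

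A reader might infer that only febrile children may be extended, or that the dosing rules can never all be followed. The documents do not support either. Fever is the only trigger they name, but they do not forbid others, and most children raise no conflict.

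A reader might also take 25% to 50% of the 4-day arm as the number affected. That does not stand. It comes from an exponential curve that already has 29% of children meeting a criterion with a 24-hour element within one day of drainage; at the same 2-day median, the Weibull curve leaves 6% unrecovered at day 4. It also counts fever extensions, which the protocol openly permits. The wording conflict can account only for afebrile children who have not met the rest of the criterion, plus febrile children whose surgeon would otherwise stop.

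Finally, the Diagram 1 flow chart could not be read here, only its footnotes, so it should be checked for a governing rule.

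**Conclusion.** The point holds in a narrow form. The stated rules conflict outright for a child who is afebrile but not yet tolerating food when the assigned course ends. They are inconsistent in force for a child still febrile, and unclear on whether the 24 hours covers fever. The readable text does not say which rule governs.

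The direction is firm: such children are at least as common at day 4 as at day 8, so any resulting extra treatment falls more on the short arm and moves the arms together. The size is not known. The contrasts of 3.96 to 2.56 days rest on assumed curves, on the IV sentence always governing, and on attributing permitted fever extensions to the conflict, so the share due to the wording is smaller. The equivalence probabilities further assume that extended children take the full 8-day risk. The effect may be small, but the wording defines the randomized exposure and should be corrected.

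**What to change.** Reconcile the Abstract, the C.1 antibiotic paragraphs, the Diagram 1 footnote and D.1 so that one rule governs the end of the assigned course for every child: febrile, afebrile but not tolerating food, and only recently recovered. State what the 24 hours modifies. Which rule applies is a clinical decision for the investigators, and none is proposed here. Then make the description of the compared regimens in the Abstract and in the hypothesis match the rule chosen.

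The cost is a protocol wording amendment and a memo to sites. It needs no extra patients, visits or procedures.
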